5. STUDY POPULATION

5.1 Description of the Study Population

A total of 85 participants will be enrolled from 3 METRC Military Treatment Facilities over a 10 month period.

Consenting procedures are described in detail in Sections 8 and 13 of this protocol.

5.1.1 Participant Inclusion Criteria

1. Ages 18-60
2. Currently one or more years out from a traumatic unilateral lower extremity injury at or below the knee

3. Healed fractures and able to fully weight bear
4. Evidence of either:
 - a. Weakness of ankle dorsiflexors and /or plantarflexors resulting from leg injury (defined as less than 4 out of 5 on manual muscle test)
 - b. Limited ankle dorsiflexion (< 10 degrees) and /or limited ankle plantarflexion (< 20 degrees) resulting from leg injury
 - c. Mechanical pain with loading to hindfoot/midfoot (\geq 50 mm on a 0-100 mm visual analogue scale assessing average daily pain)
 - d. Ankle or Hindfoot fusion or candidate for ankle or hindfoot fusion
 - e. Candidate for amputation secondary to ankle/foot impairment

5.1.2 Participant Exclusion criteria

Patients who satisfy any of the following exclusion criteria will be ineligible for enrollment in the study:

1. Ankle plantarflexion or dorsiflexion weakness as a result of spinal cord injury or central nervous system pathology.
2. Non-ambulatory
3. Surgery on study limb anticipated in next 6 months
4. Medical or psychological conditions that would preclude functional testing (ex. severe traumatic brain injury, stroke, renal failure, heart disease, severe anemia)
5. Neurologic, musculoskeletal or other conditions affecting contralateral extremity preventing the study of a healthy control limb
6. Unable or unwilling to participate in two 4-week PT programs
7. Pregnancy
8. Non-English speaking

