To maximize an individual's potential success in utilizing the IDEO, a high intensity, sports medicine based approach to rehabilitation was developed in collaboration with the departments of orthopaedics, physical therapy and orthotics/prosthetics at the Center for the Intrepid and the San Antonio Military Medical Center. The multidisciplinary Return to Run (RTR) clinical pathway focuses on strength, agility and speed with the goal of enabling patients to return to running, sports and military deployment^{21,23}. Running was chosen as a surrogate for the return to high level function based on the successes of amputation rehabilitation programs⁴². Also, working alongside similar patients who have been fitted with an IDEO provides a built-in support group and helps build self efficacy, which is one of the most important predictors of good outcomes and return to usual activity. The early success of this clinical pathway showed 80% return to running²³. In addition to success in high level rehabilitation goals, the RTR Clinical Pathway has returned wounded warriors to duty to include deployment^{21,43-44}.

Preliminary Studies to Support the Efficacy of the IDEO and RTR Clinical Pathway.

In a small study of 18 subjects with unilateral dorsiflexion and/or plantarflexion weakness, the functional performance of the IDEO was compared against two commercially available orthoses and no orthosis. All participants in this study also completed physical therapy component of the Return to Run Clinical Pathway. Performance wearing the IDEO was compared to that wearing the Allard BlueRocker™ (BR), a rigid plastic posterior leaf spring (PLS), and no brace (NONE)²². Subjects were evaluated on six functional tests wearing the IDEO, BR, PLS, and NONE. Brace order was randomized and 5 trials were completed for each measure. Performance was

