significantly better in the IDEO on all functional measures compared to all other bracing conditions ($p < 0.004$), with the exception of the sit-to-stand five times, in which there was only a significant improvement against the BR ($p = 0.014$). The forty yard dash improved by 37% over the PLS and NONE, and by 28% over the BR. The BR demonstrated a significant improvement in the forty yard dash compared to NONE ($p = 0.033$), and self-selected walking velocity on level terrain over NONE and PLS ($p < 0.028$), but no significant difference was found between the PLS, BR and NONE in any other functional measure. This study did not, however, evaluate the impact on patient reported outcomes of the improvements in functional performance⁴³.

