Following 2-4 weeks of home PT (T1), the participant will be fitted with the IDEO and engage in four weeks of Post-IDEO PT at the study center. During these 4 weeks, adjustments to the brace will be made and the participants will learn how to optimize the use of the brace.

At the end of the four weeks of post-IDEO PT (T2), performance testing will be repeated and overall satisfaction with the device assessed. The purpose of these assessments is to measure any immediate gains in function. Participants will then be formally ‘discharged’ from the PRIORITI program. They will be given the number of the Study Site Orthotist to call if any concerns arise with the IDEO and its fit. The costs associated with all visits to the orthotist during the 12 month follow-up period will be covered by the study.

At 6 months following the completion of the PRIORITI program (T3), participants will be contacted by the Study Coordinator and asked to participate in a brief interview by phone. The main purpose of this phone call is to keep participants engaged in the study and motivate them to come back to the hospital for the final visit at 12 months. We will also use this opportunity to ask them questions about their functioning, satisfaction with the brace and use of services (overall and specific to the IDEO). This interview will last about 15 minutes. During the call the he coordinator will remind the participant of the 12 month follow up visit. If the participant is living outside of the research site area, the coordinator will inform the participant that travel expenses can be covered for the 12 month follow up visit. (See appendix K).

At 12 months following the completion of the PRIORITI program (T4), participants will be asked to return to the Study Center to repeat the performance tests and self reported measures of outcome and satisfaction with the IDEO. Additional questions regarding use of services (overall and specific to the IDEO) will also be asked.

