5.2 Strategies for Recruitment and Screening

Eligible study participants will be identified in several ways as outlined below.

The study center will reach out to orthopaedic surgeons, physical medicine and rehabilitation physicians and physical therapists practicing in the military and veterans community to educate them about the study and ask for referrals of patients they believe may meet the inclusion and exclusion criteria.

The participating study centers will query their orthopaedic registries and identify patients they treated one or more years ago for a severe traumatic lower extremity injury. These individuals will be sent a letter and brochure (explaining the study, its risks and requirements) from their treating physician or the director of orthopaedics if their treating physician is no longer practicing at the facility, and encouraged to contact the center if they think they meet the study criteria (See Appendix H for draft).

We will mount a direct advertising campaign to include local radio and newspaper advertisement, targeting appropriate media outlets frequented by service members and veterans. These advertisements may be produced locally or by the METRC Coordinating Center to maximize our target audience. We will also launch a social media campaign, using the advertisement attached as Appendix J. This advertisement directs potential participants to the PRIORITI website where they are able to access additional information and use our eligibility application. www.prioriti-mtf.org

- **LinkedIn**
There are several groups we would like to utilize on LinkedIn for the purposes of posting our advertisement. The only contact information on the ad is the PRIORITI website. We do not intend to facilitate forum discussions, rather interested participants will be directed to the PRIORITI website. The groups we intend to target are the following:
 - US Military Veterans Network
 - Wounded Warrior Project
 - Society of Orthotics and Prosthetics
 - Disabled American Veterans
 - Stryker, Inc.
 - Hanger, Inc.
 - Orthopaedic Trauma Association
 - Society for Orthotics and Prosthetics
 - The Trauma Network
 - The Lower Extremity Review
 - US Department of Veterans Affairs

- **Twitter**

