APPENDIX C: DATA COLLECTION SCHEDULE

	TIME 0	T2	T3	T4
Assessment	Baseline			
Patient Characteristics				
Demographics	X			
Marital Status & Social Support (MSPS)	X			
Self Efficacy	X			X
Income (past year) & Health Insurance	X			X
Injury Characteristics				
Mechanism, Type, Side of Injury	X			
Classification of Fx (AO/OTA & Gustilo)	X			
Other limb and non limb injuries	X			
Medical History and Clinical Assessment				
Height and Weight	X			X
Co-morbidities & Smoking History	X			
Fracture Healing	X			
Evidence of PTOA (from x-rays)	X			
ROM and Strength of Lower limbs	X			X
VAS Pain and Use of Narcotics	X			X
Outcomes: Performance Assessments				
4 Square Step Test	X	X		X
Illinois Agility Test	X	X		X
Sit to Stand	X	X		X
Timed Stair Ascent	X	X		X
Self Selected Walking Speed	X	X		X
Shuttle Run	X	X		X
Single Leg Stance	X	X		X
Outcomes: Self Reported Measures				
Short Musculo Func Assess (SMFA)	X		X	X
Veterans Health Survey (VR-12)	X		X	X
Paffenbarger Activity Scale (PPAQ)	X			X
Brief Pain Inventory (BPI)	X			X
Usual Major Activity Status	X		X	X
If working: Work Productivity (WPAI)	X		X	X
Depression Scale of PHQ (PHQ-9)	X			X
PTSD Checklist (PCL)	X			X
Use and Satisfaction with IDEO				
Satisfaction with Brace (OPUS & CFI)	X	X	X	X
Use of Brace, Shoe Wear , Ambulatory Aids	X	X	X	X
Use of Services and Aids				
Hospitalizations	X		X	X
Orthotic Services	X		X	X
PT/OT Services	X		X	X
Other Services	X		X	X
Treatment Logs Maintained by CPO & PTs				

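### Nothing keeps out or identifies people who already had an IDEO or Return to Run, and no orthosis condition is set for the performance tests, so T0 need not be a true before-measurement

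*Combined protocol and SAP*

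**What the plan says.** **Eligibility.** Section 5.1.1 requires "Currently one or more years out from a traumatic unilateral lower extremity injury at or below the knee" and sets no upper limit on time since injury and no condition on earlier orthotic treatment. Section 5.1.2 opens with "Patients who satisfy any of the following exclusion criteria will be ineligible for enrollment in the study" and lists eight items; none mentions an earlier IDEO or earlier Return to Run therapy. The Protocol Summary repeats both lists.

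**Screening.** The self-check in section 5.2, the telephone screen in 6.1.1 (injury, initial treatment and SMFA) and the in-person screen in 6.1.2 (clinical assessment, medical history and interview) do not list the question either.

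**Recruitment.** Besides referral and advertising, section 5.2 has the centers "query their orthopaedic registries and identify patients they treated one or more years ago for a severe traumatic lower extremity injury".

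**Earlier use.** Section 2.1 describes 18 subjects tested in the IDEO, all of whom completed the pathway's physical therapy. It also says "The early success of this clinical pathway showed 80% return to running", and reports return to duty including deployment.

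**Test condition.** Section 4 describes the T0 battery without naming an orthosis; for T2 it says that "performance testing will be repeated and overall satisfaction with the device assessed". Sections 6.2.2 and 6.3.1 list the tests only. In the test descriptions of 6.4.1, the only wording about aids concerns optional assistive devices in the walking test, whose use is recorded, and the stair railing.

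**Brace data.** Appendix C marks the row "Use of Brace, Shoe Wear , Ambulatory Aids" at T0, but the T0 interview list in 6.2.3 has shoe wear and ambulatory aids without brace use.

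**The concern.** With no comparison arm, the whole effect estimate is the difference between a later visit and T0. It measures the program only if T0 reflects the state before the program's two components, which section 7 defines as the IDEO and Return to Run.

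A person fitted with an IDEO some years ago who still has ankle weakness, limited motion or a fusion can meet every criterion. If that person is tested at T0 in their own IDEO, much of the benefit is already in the baseline and the change is too small. If the same person is tested unbraced at T0 and in the IDEO at T2, the change includes a device gain that this study did not produce. Someone who has already completed Return to Run may likewise have taken part of the therapy gain before T0.

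Because the test condition is neither fixed nor recorded, the direction of the error could not be established afterwards. The functional performance part of the primary endpoint is affected at both T2 and T4.

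**Working it through.** **1. The plan's own figure.** Inputs from section 10.2: 80 complete participants, one-sided paired t-test, 80% power, detectable effect 0.28 (mean change divided by SD of change). Alpha is not stated.

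- One-sided 0.05: (1.645 + 0.842) / √80 = 2.486 / 8.944 = 0.278. Exact noncentral-t power at 0.28 is 79.9%.
- Two-sided 0.05: (1.960 + 0.842) / 8.944 = 0.313.

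The stated 0.28 therefore reproduces with one-sided 0.05, which is assumed below.

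**2. Dilution.** Let a share f be prior users tested at T0 in their own IDEO, with no further gain. The others have true effect d, and the SD of change within each group is 1. Then

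mean = (1 − f)d; SD = √(1 + f(1 − f)d²); standardized effect = mean / SD.

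The documents give no value for f, so a range is shown.

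| d | f | Mean change | Standardized | Power (n = 80) |
|---|---|---|---|---|
| 0.28 | 0 | 0.280 | 0.280 | 80% |
| 0.28 | 5% | 0.266 | 0.266 | 76% |
| 0.28 | 10% | 0.252 | 0.251 | 72% |
| 0.28 | 20% | 0.224 | 0.223 | 63% |
| 0.60 | 20% | 0.480 | 0.467 | 99% |

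**3. Inflation.** Suppose nobody truly changes, but a share f are prior users tested unbraced at T0 and in the IDEO at T2, which shifts their score by s. Then mean = f·s and SD = √(1 + f(1 − f)s²). For s the range 0.6 to 1.0 is used. These are the effect sizes that section 10.2 quotes from the preliminary brace comparison, borrowed here only as an illustration of a device shift.

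| f | Standardized effect, s = 0.6 to 1.0 | Chance of a significant improvement (nominal 5%) |
|---|---|---|
| 5% | 0.030 to 0.049 | 8% to 11% |
| 10% | 0.059 to 0.096 | 13% to 21% |
| 20% | 0.117 to 0.186 | 27% to 50% |

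**4. Could the planned data repair this?** Section 6.2.3 records orthotic services in the past year, which misses an earlier fitting. The exploratory regressions in 10.6 name patient and injury characteristics, baseline impairment and PT attendance. They do not name prior IDEO, prior Return to Run or the orthosis worn at T0.

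**The case against.** **Prior users may be few or absent.** Section 2.2 places the earlier studies at one facility, and 7.1 has orthotists from the other two facilities learn fabrication before taking the program home. Each center searches its own registry. Whether the originating center enrols is unclear: the Protocol Summary gives three sites and a setting beyond that center, while section 7 speaks of two participating sites. This stands. Exposure is possible but not shown, and its share is unknown.

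**0.28 is the detectable effect, not the expected one.** This also stands. At a true effect of 0.6, even 20% prior users leave power at 99%; the estimate would still be too low (0.48).

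**For brace-naive participants the device gain is part of the intervention.** Correct. Unbraced at T0 and in the IDEO at T2 is not in itself a bias for them, so the inflation figures apply to prior users only.

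**Other material may cover it.** Section 11.1 refers to a manual, and draft case report forms are listed but not in the reviewed text. A test condition could be stated there.

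Three stronger readings are tempting, and the documents do not support them:

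- From "The forty yard dash improved by 37% over the PLS and NONE, and by 28% over the BR" a reader might infer that 9 points, about a quarter of the gain, depend on what is worn at T0. The gain is the same over the leaf spring and over no brace, and section 2.1 calls the leaf spring type the main option for these patients. The gap arises only for wearers of the other commercial brace. Section 6.4.1 also describes a 10 meter shuttle run, not that dash.
- From the T0 mark in Appendix C a reader might infer that participants arrive braced. The row sits under an IDEO heading, and 6.2.3 and 6.4.2 do not place brace use at T0, so the mark may be a table inconsistency.
- A reader might suppose that prior users would enrol to obtain a replacement brace. Nothing in the documents says so.

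**Conclusion.** The point holds as a design gap. A site could follow the plan exactly and enrol someone whose T0 is not a before-measurement, and the supplied text neither fixes nor records the orthosis worn during testing. For prior users the bias can go either way.

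Its size cannot be derived from the documents. The figures above rest on an assumed share of prior users, one-sided alpha of 0.05, unit SD of change within groups and, for inflation, a borrowed device shift. As an illustration, 10% prior users with no gain turn 0.28 into 0.25 and 80% power into 72%. The documents do not show that the results will be biased by any particular amount, or that prior users will enrol in number. The sample-size calculation is sound on its own inputs. The change is worth making because it is cheap, and because an unrecorded T0 condition cannot be recovered later.

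**What to change.** 1. Add one exclusion to section 5.1.2 and the Protocol Summary: previously fitted with an IDEO, or previously completed Return to Run. Ask it at the telephone screen in 6.1.1. If such people are already enrolled, flag them and report Aims 1 and 2 with and without them.
2. In 6.2.2 and 6.3.1, state one orthosis condition per visit, the same at all sites: for example, the usual orthosis, if any, at T0 and the IDEO at T2. The T4 condition decides whether stopping use of the IDEO counts in the result; that is an estimand choice for the sponsor to state.
3. Record the type of orthosis worn during testing at T0, T2 and T4.
4. Reconcile the T0 brace-use mark in Appendix C with the interview list in 6.2.3.

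Cost: one exclusion line, one screening question, a few sentences and one case report form field. The recruitment pool shrinks slightly, mainly if the originating center enrols. The planned sample size and the detectable effect of 0.28 are unchanged.

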5.1.3 Co-Enrollment Guidelines

We do not anticipate this patient population will be eligible for other METRC studies.

5.2 Strategies for Recruitment and Screening

Eligible study participants will be identified in several ways as outlined below.

The study center will reach out to orthopaedic surgeons, physical medicine and rehabilitation physicians and physical therapists practicing in the military and veterans community to educate them about the study and ask for referrals of patients they believe may meet the inclusion and exclusion criteria.

The participating study centers will query their orthopaedic registries and identify patients they treated one or more years ago for a severe traumatic lower extremity injury. These individuals will be sent a letter and brochure (explaining the study, its risks and requirements) from their treating physician or the director of orthopaedics if their treating physician is no longer practicing at the facility, and encouraged to contact the center if they think they meet the study criteria (See Appendix H for draft).

We will mount a direct advertising campaign to include local radio and newspaper advertisement, targeting appropriate media outlets frequented by service members and veterans. These advertisements may be produced locally or by the METRC Coordinating Center to maximize our target audience. We will also launch a social media campaign, using the advertisement attached as Appendix J. This advertisement directs potential participants to the PRIORITI website where they are able to access additional information and use our eligibility application. www.prioriti-mtf.org

- **LinkedIn**
There are several groups we would like to utilize on LinkedIn for the purposes of posting our advertisement. The only contact information on the ad is the PRIORITI website. We do not intend to facilitate forum discussions, rather interested participants will be directed to the PRIORITI website. The groups we intend to target are the following:
 - US Military Veterans Network
 - Wounded Warrior Project
 - Society of Orthotics and Prosthetics
 - Disabled American Veterans
 - Stryker, Inc.
 - Hanger, Inc.
 - Orthopaedic Trauma Association
 - Society for Orthotics and Prosthetics
 - The Trauma Network
 - The Lower Extremity Review
 - US Department of Veterans Affairs

- **Twitter**
We will use a Twitter account to tweet study inclusion information to selected groups and members. We will contact respected members of those groups (Surgeons, Military personnel etc) and request that they retweet our invitation to be involved in the study. Tweets will contain a unique URL directing participants to the PRIORITI Website.

- **Magazine Advertisements**
We plan to purchase a ¼ to ½ page advertisement (Appendix J) that will be printed in various Veterans magazines. Three magazines we plan to target are:
 - Disabled American Veterans
 - American Veteran Magazine (AMVETS)
 - The Journal

- **Blogs**
There are blogs we would like to utilize for the purpose of posting our advertisement. The only contact information on the ad is the PRIORITI website. We do not

intend to facilitate forum discussions, rather interested participants will be directed to the PRIORITI website. The groups we intend to target are the following:

- <http://americanveteranmagazine.blogspot.com/>
- <http://www.blogs.va.gov/VAntage/>
- <http://warriorcare.dodlive.mil/>

- YouTube
We have an approved recruitment video that is currently posted on the PRIORITI Website. We would like to post the video on YouTube. Prior to posting we would modify the video such that the introduction specifies that interested parties should visit the PRIORITI website for more information and confirmation of eligibility.

- Local Radio Advertisements
We will utilize the radio script to create a radio advertisement. Both the MCC and local sites will be permitted to run this advertisement on radio stations to broaden the scope of our recruitment efforts. (Appendix G)

- Local News Paper Advertisement
The MCC and local sites will place the approved advertisement (Appendix J) in local newspapers.

- Facebook
We will initiate an IDEO brace Facebook page. We will use the IDEO logo as the profile photo and a picture of the brace on a leg as the background photo. The page will use approved advertisement verbiage to provide potential participants with information about the study and brace. Interested participants will be directed to www.PRIORITI-MTF.org. We will adjust the privacy settings such that any “wall posts” will require approval by the page editor (a member of the MCC staff).

To assist in recruitment, a printed brochure and a video are being produced that describe the IDEO and PRIORITI program, the goals of the study, who is potentially eligible for the study and what would be expected of individuals who agree to participate in the study. The recruitment materials will be produced in collaboration with communications experts as well as 1-2 consumers who meet the general inclusion criteria for the study. All recruitment materials will be made available on a website, www.prioriti-mtf.org. This website will also be accessible through the METRC website, www.METRC.org. (A draft of the video script is included in J).

The goal is to develop an effective but efficient process of finding potentially eligible individuals for the study. Individuals who learn about the study through any of the methods described above will be encouraged to contact the local study center *if* they meet the following criteria:

- ✓ Is between the ages of 18 and 60 and able to walk (with or without an assistive device)

- ✓ Had a traumatic injury to their leg (at or below the knee) one or more years ago for which they were initially hospitalized overnight in a hospital
- ✓ Can answer yes to one or more of the following questions:
 - Are you limited in what or how much you are able to do at home, at work or at school because of your leg injury?
 - Are you limited in the types or frequency of sports and recreational activities you would like to do because of your leg injury?
 - Are you dissatisfied with the recovery you have made from your leg injury?

